7.2.3.1.2. Doxorubicin

7.2.3.1.2.1. Hematologic Toxicity

Doxorubicin will not be administered after the initial dose if the patient's ANC is <1000 cells/ μL or if the platelet count is $<100,000$ cells/ μL . When necessary, the next treatment cycle should be delayed until the ANC is ≥ 1000 cells/ μL and the platelet count is $\geq 100,000$ cells/ μL and nonhematologic toxicities have resolved. For patients who experience \geq Grade 3 neutropenic fever or infection or Grade 4 neutropenia without fever lasting more than 1 week, doxorubicin should be reduced to 75% of the starting dose (that is, to approximately 60 mg/ m^2). If a patient experiences a second incidence of neutropenic fever/infection or has another episode of Grade 4 neutropenia lasting >1 week, then a second dose reduction to 45 mg/ m^2 will be necessary. Therapeutic and prophylactic use of pegfilgrastim (Neulasta[®]) or other G-CSFs will be allowed per current American Society of Clinical Oncology (ASCO; Smith et al. 2006) and National Comprehensive Cancer Network (NCCN) guidelines (NCCN 2014). For patients with Grade 4 ANC without fever/infection lasting less than 1 week, retreatment will be allowed at the investigator's discretion with the full dose of doxorubicin (75 mg/ m^2) with recommended use of

G-CSFs per current ASCO guidelines (Smith et al. 2006). See [Table JGDM.4](#) for doxorubicin dose modification for neutropenia.

Table JGDM.4. General Guidelines for Doxorubicin Dose Modification Due to Neutropenia

Toxicity	Required Dose Modification
ANC <1000 cells/ μ L	No doxorubicin administered; treatment cycle delayed.
At pretreatment:	
If Grade ≥ 3 neutropenic fever/infection has occurred	Approximately 60 mg/m ² doxorubicin.
If Grade 4 neutropenia lasting longer than 1 week has occurred	Approximately 60 mg/m ² doxorubicin.
Grade 4 ANC without fever/infection	Retreatment with doxorubicin at full dose at investigator's discretion with recommended use of prophylactic G-CSFs.
Second incidence of either:	
1) Grade ≥ 3 neutropenic fever/infection	Second dose reduction to 45 mg/m ² .
2) Grade 4 neutropenia lasting longer than 1 week	

Abbreviations: ANC = absolute neutrophil count; G-CSF = granulocyte colony-stimulating factor.

7.2.3.1.2.2. Cardiovascular Toxicity

Cardiotoxicity is a recognized risk of doxorubicin that increases with higher cumulative drug exposure. Cardiac monitoring is conducted by a combination of monitoring of clinical parameters, ECG, and ECHO/MUGA scans.

Electrocardiogram changes, arrhythmias, tachycardia, and/or chest pain should be managed according to clinical practice based on the specific findings.

Patients will undergo baseline LVEF determination by ECHO or MUGA scan. This evaluation may be repeated at any time during the study if clinically indicated. If there is a decrease in LVEF of $\geq 10\%$ and below the lower limit of normal, if there is an absolute decrease of 20%, or if the absolute LVEF decreases to or below 40%, then doxorubicin will be discontinued. Doxorubicin should also be discontinued if the patient develops Grade 3 or 4 left ventricular systolic dysfunction (symptomatic congestive heart failure). All such changes should be reported as AEs. If doxorubicin is discontinued for the above changes in LVEF, then olaratumab must be discontinued as well (see Section [7.2.3.1](#)).

The diagnostic method used at baseline for cardiovascular assessments (for example, ECHO or MUGA scans) should be the same method used throughout the study, unless there is clinical or instrumental evidence that further investigations are needed.

7.2.3.1.2.3. Hepatic Impairment

Doxorubicin is contraindicated in patients with severe hepatic impairment (Child-Pugh Class C or total serum bilirubin >5.0 mg/dL). Refer to Section [7.2.3.1](#) for additional information.

7.2.3.1.2.4. Nonhematologic Toxicity

Permanent discontinuation of doxorubicin should be considered for any patient experiencing Grade 4 nonhematologic toxicity assessed as related to doxorubicin. If the investigator feels re-dosing of doxorubicin is appropriate (except for Grade 4 cardiotoxicities and Grade 4 bilirubin increase which require mandatory discontinuation [see Section 7.2.3.1.2.2 and Section 7.2.3.1.2.3]), treatment may only resume after consultation with the Lilly study physician, with the dose reduced to 60 mg/m² (or less if agreed by the investigator and Lilly physician). If Grade 4 toxicity recurs after therapy resumes, doxorubicin treatment will be permanently discontinued.

For appropriate management of cardiac toxicities and hepatic impairment, refer to Section 7.2.3.1.2.2 and Section 7.2.3.1.2.3.

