Any patient who requires a dose reduction will continue to receive the reduced dose for the remainder of the study. Any patient who has had 2 dose reductions and who experiences a toxicity that would cause a third dose reduction must be discontinued from study drug.

In the event of an alteration in olaratumab dose due to an olaratumab-related toxicity, doxorubicin need not be altered, and the planned doxorubicin schedule should be maintained.

Similarly, olaratumab therapy need not be altered for doxorubicin-related toxicity. An alteration in doxorubicin dose will always necessitate a corresponding change to dexrazoxane, if administered, in order to maintain a dosage ratio of 10:1 (dexrazoxane:doxorubicin).

Discontinuations:

In general, discontinuation of olaratumab will not necessitate discontinuation of doxorubicin. In the event of discontinuation of olaratumab therapy due to an olaratumab-related toxicity or Grade 3 or 4 IRR, doxorubicin need not be altered, and the planned doxorubicin schedule may be maintained at the discretion of the investigator. Discontinuation of doxorubicin will necessitate discontinuation of olaratumab.

Any changes in treatments being added to or removed from patient care will be recorded on the eCRF.

The following information (in this section and the following subsections) pertains to dose modifications and delays for and management of AEs of concern, which may or may not be associated with olaratumab therapy, including the following:

- IRR (see Section 7.2.3.1.1.1)
- Hematologic toxicity (see Section 7.2.3.1.1.2)
- Nonhematologic toxicity (see Section 7.2.3.1.1.3)

The following information (in this section and the following subsections) pertains to dose modifications and delays for and management of AEs of concern, which may or may not be associated with doxorubicin therapy, including the following:

- Hematologic toxicity (see Section 7.2.3.1.2.1)
- Cardiovascular toxicity (see Section 7.2.3.1.2.2)
- Hepatic impairment (see Section 7.2.3.1.2.3)
- Nonhematologic toxicity (Section 7.2.3.1.2.4)

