7.3.1. Selection and Timing of Doses

A cycle is defined as an interval of 21 days (a cycle may be delayed up to 3 days due to holidays, weekends, bad weather, or other unforeseen circumstances without being counted as a protocol deviation).

The dose of olaratumab to be administered will be determined by measuring the patient's weight in kilograms on Day 1 and Day 8 of each cycle. The dose of doxorubicin to be administered will be determined by calculating the patient's body surface area at the beginning of each cycle. If the patient's weight does not fluctuate by $\geq 10\%$ (increase or decrease) from the weight used to calculate the prior dose, the olaratumab dose will not need to be recalculated. A $\pm 5\%$ variance in the calculated total dose will be allowed for ease of dose administration.

A patient may continue to receive study treatment until he or she has received a maximum of 6 cycles of olaratumab in combination with doxorubicin, or until he or she meets 1 or more of the specified reasons for discontinuation (as described in Section 6.3.2).

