7.5.1.1. Dexrazoxane

Starting with the first cycle of combination therapy (that is, Cycle 2), dexrazoxane may be administered IV at the investigator's discretion according to instructions provided in the pharmacy manual for this study, beginning within 30 minutes prior to each doxorubicin infusion for the prevention of cardiotoxicity. It is recommended that all patients receiving 5 or more cycles of doxorubicin receive dexrazoxane. Investigators should consult the dexrazoxane information provided in the pharmacy manual for this study for administration information (including warnings, precautions, contraindications, adverse reactions, and dose modifications).

As the dose of dexrazoxane administered is dependent on the dose of doxorubicin administered, any dose modifications to doxorubicin will require a corresponding dose modification to dexrazoxane in order to maintain a dosage ratio of 10:1 (dexrazoxane:doxorubicin).

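### The first doxorubicin reduction for neutropenia is given as 75% of the starting dose and as about 60 mg/m², but 60 is 80% of 75; the percentage is almost certainly the wrong figure

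*Protocol*

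**What the plan says.** The doxorubicin starting dose is 75 mg/m² on Day 1 of Cycles 2 to 7 (Protocol Section 6.2 and Table JGDM.1). The neutropenia paragraph itself names 75 mg/m² as the full dose.

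The first reduction applies after Grade 3 or higher neutropenic fever or infection, or after afebrile Grade 4 neutropenia lasting more than a week. Section 7.2.3.1.2.1 says that "doxorubicin should be reduced to 75% of the starting dose (that is, to approximately 60" mg/m². For a second such episode the text is "then a second dose reduction to 45" mg/m².

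Table JGDM.4, to which the paragraph refers the reader, gives the first step as about 60 mg/m² in two rows, with no percentage. Section 7.2.3.1.2.4 covers a different situation, re-dosing after Grade 4 nonhematologic toxicity. It uses the same number without a qualifier: "treatment may only resume after consultation with the Lilly study physician, with the dose reduced to 60" mg/m², or less by agreement.

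Two other rules decide how far a difference would carry. Section 7.2.3.1: "Any patient who requires a dose reduction will continue to receive the reduced dose for the remainder of the study". Section 7.5.1.1: "any dose modifications to doxorubicin will require a corresponding dose modification to dexrazoxane in order to maintain a dosage ratio of 10:1".

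**The concern.** The sentence states the reduced dose twice, as a percentage and as an amount, and joins the two with *that is*, so the reader is told they are the same dose. They are not.

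This is an operative instruction for a cytotoxic drug, used just after a serious hematologic toxicity. A pharmacist working from the percentage and one working from the amount would prepare different doses for the same patient. The difference would persist, because a reduced dose is not raised again, and it would pass to dexrazoxane where that is given. SAP Section 5.6 lists dosing errors among its examples of important protocol deviations, so the target dose should not depend on which half of a sentence is read.

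**Working it through.** **Inputs.** Starting dose 75 mg/m² (Protocol Section 6.2). First reduction 75% and about 60 mg/m² (Section 7.2.3.1.2.1). Second reduction 45 mg/m² (same section). Dexrazoxane ratio 10:1 (Section 7.5.1.1). At most six doxorubicin cycles: "a maximum of 6 cycles of olaratumab in combination with doxorubicin" (Section 7.3.1).

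**Can the plan's figure be reproduced?** No.
- 75% of the start: 0.75 × 75 = 56.25 mg/m².
- 60 as a share of the start: 60 / 75 = 0.80, that is 80%.
- Start for which 60 would be 75%: 60 / 0.75 = 80 mg/m². The protocol uses no such dose.
- Rounding: 56.25 becomes 56 to the nearest 1 and 55 to the nearest 5. It becomes 60 only to the nearest 10 or 15, and the protocol states no such rounding.

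**Which figure is wrong?** The absolute doses all agree:

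| Place | First-step dose | Percentage given |
|---|---|---|
| Section 7.2.3.1.2.1, text | about 60 mg/m² | 75% |
| Table JGDM.4, fever/infection row | about 60 mg/m² | none |
| Table JGDM.4, prolonged Grade 4 row | about 60 mg/m² | none |
| Section 7.2.3.1.2.4 (separate rule) | 60 mg/m² | none |

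The percentage appears once in a doxorubicin dose rule, and 56.25 never appears. The second step does not discriminate: 45 fits equal steps of 15 (75 − 60 = 15; 60 − 45 = 15), and it also equals 0.75 × 60.

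**Size, if a site dosed from the percentage.**
- Per reduced dose: 60 − 56.25 = 3.75 mg/m², which is 3.75 / 60 = 6.25% below the printed dose.
- In milligrams, for an assumed body surface area of 1.5 to 2.0 m² (not given in the documents): 3.75 × 1.5 = 5.6 mg to 3.75 × 2.0 = 7.5 mg.
- Largest cumulative gap, with one full dose and five reduced doses: 75 + 5 × 60 = 375 against 75 + 5 × 56.25 = 356.25. The difference is 18.75 mg/m². Against the planned 6 × 75 = 450 mg/m², that is 18.75 / 450 = 4.2%.
- Dexrazoxane, if used: 10 × 60 = 600 against 10 × 56.25 = 562.5, a gap of 37.5 mg/m² per dose.

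**Effect on the analyses.** The primary comparison uses baseline and post-monotherapy samples, the latter taken before the first Cycle 2 dose and so before any doxorubicin. SAP Section 5.11.1 derives planned doxorubicin intensity from the full dose (75 / 3 = 25 mg/m² per week). SAP Section 5.3.4 takes dose reductions as recorded on the eCRF. None of these uses the 75% factor.

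**The case against.** The best defence is that the sentence says *approximately*, a word the protocol does not define, and that the dose to give is clear anyway. A site would have to pass over the amount in the same sentence and in the table, and calculate for itself, to arrive at 56.25. If it did, the error would be toward a lower dose in a patient who has just had severe neutropenia. The second step is 45 mg/m² on either reading. All of this stands, and it is why the point is minor. It does not make the sentence right: *approximately* cannot turn 80% into 75% without a rounding rule the protocol does not contain.

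A reader might infer two stronger points, and the documents support neither.

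- *That 60 mg/m² fails the protocol's own dosing tolerance.* Section 7.3.1 permits a ±5% "variance in the calculated total dose will be allowed for ease of dose administration". Around 56.25 that gives 53.44 to 59.06, which excludes 60; around 60 it gives 57.00 to 63.00, which excludes 56.25. But this is an allowance for preparing a dose once the level is fixed. It does not define *approximately*. It also follows directly on the olaratumab recalculation rule, so applying it to doxorubicin is an inference. The mismatch does not depend on it.
- *That the intended dose is open.* One could argue that *approximately* would be needless if 80% were meant, since 0.80 × 75 is exactly 60. That is weak, because Table JGDM.4 uses the same qualifier with no percentage beside it. Every absolute figure points to 60.

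**Conclusion.** Wrong as written, with a minor effect. The percentage and the dose in one instruction disagree by 5 percentage points of the starting dose (75% against 80%), and the 75% is almost certainly the wrong figure. That conclusion on intent rests on the consistent 60 mg/m² elsewhere; the protocol does not state the intent outright.

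The size is 3.75 mg/m² per reduced dose, and only at a site that doses from the percentage. The 18.75 mg/m² cumulative figure is a worst case: it also needs a qualifying event in Cycle 2, all five later doses given, and no second reduction. The dexrazoxane gap needs discretionary dexrazoxane to be in use. Nothing here touches the sample size or the definition of any analysis, and the documents give no ground for claiming that patients would be overdosed.

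**What to change.** In Protocol Section 7.2.3.1.2.1, either delete the reference to 75% of the starting dose or change it to 80%, and state 60 mg/m² so that the text matches Table JGDM.4. Deleting the percentage is cleaner, because the table carries none.

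The sponsor should confirm 60 mg/m² when making the edit. In the unlikely event that 75% was intended, the sentence and both first-reduction rows of the table would have to change to about 56 mg/m² instead.

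The cost is one phrase in the protocol and one confirmation. Sample size, data collection and the SAP are unchanged.

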7.3. Method of Assignment to Treatment

Patients who meet all criteria for enrollment will be assigned to receive treatment. After the patient signs the ICF, the site will register the patient in the Interactive Web Response System (IWRS), which is web-based and accessible 24 hours a day. The IWRS registration consists of assigning the patient a unique study identification number. Once the patient is registered through the IWRS, he/she is considered to be enrolled in the study.

7.3.1. Selection and Timing of Doses

A cycle is defined as an interval of 21 days (a cycle may be delayed up to 3 days due to holidays, weekends, bad weather, or other unforeseen circumstances without being counted as a protocol deviation).

The dose of olaratumab to be administered will be determined by measuring the patient's weight in kilograms on Day 1 and Day 8 of each cycle. The dose of doxorubicin to be administered will be determined by calculating the patient's body surface area at the beginning of each cycle. If the patient's weight does not fluctuate by $\geq 10\%$ (increase or decrease) from the weight used to calculate the prior dose, the olaratumab dose will not need to be recalculated. A $\pm 5\%$ variance in the calculated total dose will be allowed for ease of dose administration.

A patient may continue to receive study treatment until he or she has received a maximum of 6 cycles of olaratumab in combination with doxorubicin, or until he or she meets 1 or more of the specified reasons for discontinuation (as described in Section 6.3.2).

7.4. Blinding

This is an open-label study.

7.5. Concomitant Therapy

All concomitant medications should be recorded throughout the patient's participation in the study.

Concomitant medications and supportive care therapies must also be documented at the time of discontinuation and at the 30-day short-term follow-up visit.

With the exceptions listed in the sections below, no other chemotherapy, investigational medications, other anticancer therapy, immunotherapy, hormonal cancer therapy, radiation therapy, surgery for cancer, or investigational medications will be permitted while patients are on study treatment.

Bisphosphonate osteoclast inhibitors (for example, zoledronic acid or pamidronate) for treatment of bone metastases will be permitted while patients are on study treatment. However, the osteoclast inhibitor denosumab is a monoclonal antibody and could confound safety analysis in the study if the patient experiences a hypersensitivity reaction to denosumab. Therefore, concomitant use of denosumab will not be permitted.

Appropriate documentation for all forms of premedications, supportive care, and concomitant medications (for example, medications such as sedatives, antibiotics, analgesics, antihistamines, corticosteroids, or erythropoietin; procedures such as paracentesis, or thoracentesis; or blood products such as blood cells, platelets, or fresh frozen plasma transfusions) must be captured on the eCRF.

If doxorubicin premedication is required prior to the doxorubicin infusion, this must be done after the completion of olaratumab infusion, not before the olaratumab infusion.

7.5.1. Supportive Care

Patients should receive full supportive care, if necessary. Patients will receive supportive care as judged by their treating physician. If it is unclear whether a therapy should be regarded as supportive care, the investigator should consult with the Lilly CRP. Use of any supportive care therapy must be captured on the eCRFs.

7.5.1.1. Dexrazoxane

Starting with the first cycle of combination therapy (that is, Cycle 2), dexrazoxane may be administered IV at the investigator's discretion according to instructions provided in the pharmacy manual for this study, beginning within 30 minutes prior to each doxorubicin infusion for the prevention of cardiotoxicity. It is recommended that all patients receiving 5 or more cycles of doxorubicin receive dexrazoxane. Investigators should consult the dexrazoxane information provided in the pharmacy manual for this study for administration information (including warnings, precautions, contraindications, adverse reactions, and dose modifications).

As the dose of dexrazoxane administered is dependent on the dose of doxorubicin administered, any dose modifications to doxorubicin will require a corresponding dose modification to dexrazoxane in order to maintain a dosage ratio of 10:1 (dexrazoxane:doxorubicin).

7.5.1.2. Granulocyte-Colony Stimulating Factors and Erythroid Growth Factors

Following the first dose of doxorubicin treatment, the use of G-CSFs such as pegfilgrastim and erythroid stimulating factors (for example, erythropoietin) are permitted, including prophylactic use, during investigational therapy at the discretion of the investigator, according to ASCO guidelines (Smith et al. 2006) and NCCN guidelines (NCCN 2014).

7.5.1.3. Transfusion of Blood Products

Transfusions of red blood cells, platelets, or other blood products are permitted at the investigator's discretion, but may not be used to meet hematologic criteria for inclusion in the study (refer to Section 6.1.1, inclusion criterion #9).

7.5.1.4. Anti-emetic Therapy

Both prophylactic and symptom-directed anti-emetic therapy are recommended and should be used in accordance with institutional guidelines (when existent) and/or at investigator's discretion.

7.5.2. Prohibited Therapies

Additional concurrent chemotherapy, radiation therapy, biologic response modifiers, or other investigational or approved anticancer agents may not be administered to patients on this study. Palliative radiation to symptomatic sites of disease will not be permitted while on study.

7.5.2.1. Effect of CYP3A4, CYP2D6, and P-gp Inhibitors and Inducers on Doxorubicin

Doxorubicin is a major substrate of cytochrome P450 (CYP)3A4 and CYP2D6, and P-glycoprotein (P-gp). Clinically significant interactions have been reported with inhibitors of CYP3A4, CYP2D6, and/or P-gp (for example, verapamil), resulting in increased concentration and clinical effect of doxorubicin. Inducers of CYP3A4 (for example, phenobarbital, phenytoin, St. John's Wort) and P-gp inducers may decrease the concentration of doxorubicin. Avoid concurrent use of doxorubicin with inhibitors and inducers of CYP3A4, CYP2D6, or P-gp. [Attachment 9](#) provides a list of these inhibitors and inducers.

7.6. Treatment Compliance

The study medication will be administered only at the investigational sites by the authorized study site personnel. As a result, treatment compliance is ensured. Treatment compliance will be monitored by drug accountability records, and treatment administration data are recorded in the patient's medical record and eCRF. An investigator is required to prepare, maintain, and record all observations and other data pertinent to the investigation on each individual treated in this clinical trial. All data reported on the eCRF must be derived from source documents and be consistent with the source documents.

7.6.1. Evaluable Patients

Evaluable patients are those with adequate biomarker samples who have a baseline (pre-monotherapy) and at least 1 postbaseline measurement. Patients who withdraw from the study before receiving study drug will be replaced and will not be included in the safety or primary objective assessments. Safety analyses will be conducted on all patients who have received at least 1 dose of study drug.

If the patient is noncompliant during olaratumab monotherapy (Cycle 1) and does not undergo the post-olaratumab monotherapy biopsy or the C1D1 pre-dose and C2D1 predose whole blood sample collection due to reasons other than drug-related toxicity, he or she will be considered nonevaluable for the primary objective. These patients may be replaced to ensure that 35

patients complete the pre-treatment tissue biopsy, the C1D1 pre-dose whole blood sample collection, 1 cycle of olaratumab monotherapy, and the post-olaratumab monotherapy biopsy, and the associated C2D1 predose whole blood sample collection.

8. Safety, Pharmacokinetic, Pharmacodynamic, and Efficacy Data Collection

